Official Title of Study: -

**MASSAGE WITH SENNA-BASED LAXATIVES VERSUS
SENNA-BASED LAXATIVES IN MANAGING OVERFLOW
RETENTIVE STOOL INCONTINENCE IN PEDIATRICS: A
Randomized Controlled Trial**

Document Date: - 02/12/2020.

**Human Subjects protection review board approval
date: - 03/31/2019**

MASSAGE WITH SENNA-BASED LAXATIVES VERSUS SENNA-BASED LAXATIVES IN MANAGING OVERFLOW RETENTIVE STOOL INCONTINENCE IN PEDIATRICS: A Randomized Controlled Trial

[name]

Assistant Lecturer of pediatric surgery, faculty of medicine, *South Valley University, Qena, Egypt*

[name].

Lecture of physical therapy. Department of Physical Therapy for Pediatrics, Faculty of Physical Therapy, South Valley University, Qena, Egypt

Abstract

Background: Overflow retentive stool incontinence is a common disorder affecting children that affect the quality of life in the form of shame, humiliation, depression, and decrease reduced self-esteem of children. **Aim:** To compare the effect of massage with senna-based laxatives versus senna-based laxatives in managing overflow retentive stool incontinence in pediatrics. **Methods:** Eighty-six children with overflow retentive stool incontinence enrolled in this study and were assessed for eligibility. Children's age ranged from four and fourteen. They were assigned randomly into two groups. Group (A) received abdominal massage with senna-based laxatives and group (B) received senna-based laxatives only. The application of massage was applied for 15 minutes, three times/day for six successive months. **Results:** Post-treatment there was a significant improvement in both groups in favor of massage group, $P < 0.05$. **Conclusion:** Abdominal massage with senna-based laxatives has a great effect on children with overflow retentive stool incontinence than senna-based laxatives only. **Keywords:** Overflow retentive stool incontinence, senna-based laxatives, and abdominal massage.

Introduction

Constipation is the most common colonic motility disorder in children affecting between 0.7% to 29.6 % of the pediatric population (**Rasquin 2006, Mugie 2011**) and is frequently associated with fecal incontinence secondary to overflow (**Voskuijl 2004**)

Laxatives are the main line of maintenance therapy of overflow retentive stool incontinence (ORSI) with satisfying results (**Yik 2012**) stimulant laxatives like senna based laxatives (SBL) are our standard choice in Egypt due to its availability (**Bassiuony 2015**).

Massage is the manipulation of muscles and connective tissues (CT) (superficial and deeper layers) by using different techniques. It has been practiced in many ancient civilizations for thousands of years. (**Weerapong 2005**)

Abdominal massage is a noninvasive, effective, and safe form of constipation management in the general population. (**Lamas et al. 2009, Lamas et al., 2012 and Turan&Asti 2016**) .It provides a low burden of risk, reduces symptoms of chronic constipation, improves the quality of life, decreases the use of laxatives and increases the frequency and consistency of bowel movements (**Smith and Moss, 2008; Moss et al., 2007; Richards 1998; Lamas et al., 2010**).

Subjects and methods:

This randomized controlled study was conducted in the out-patient clinic in the Faculty of Medicine, South Valley University from March 2016 to March 2019. The parents of each child submitted Informed consent. The procedures that followed had No: P.T. REC/012/002277 that approved by the Institutional Ethical Committee Clearance of the Faculty of Physical Therapy at Cairo University. The study had registration number NCT registered on Clinicaltrial.gov.

A total of one hundred and seventy children with overflow retentive stool incontinence were evaluated for eligibility. Twenty-seven children did not complete the treatment course, fifty-eight child excluded due to unresponsiveness or non-compliance to our protocol, and eighty-six child was divided randomly into two groups.

The children were selected according to these criteria: (i) Children's aged ranged from four to fourteen years, (ii) children were from both sexes, (iii) children had a history of overflow retentive stool incontinence. Other children were excluded from our study as they met one of the following criteria: (i) children had suspicion of Hirschsprung's disease, (ii) children had anorectal malformation, (iii) children had organic obstruction, (iv) children failed to complete treatment (if cramping abdominal pain or vomiting occurred), (v) children required bowel surgery.

Group A: Senna based laxative

Initial cleanout protocol for dis-impaction of the colon with the administration of one or two enemas per day with 20 ccs/Kg warm tap water with a salt enema (0.9 % saline can be made by adding 1.5 teaspoons of salt to 960 ml of water) (**Levitt 2010**) till been clean by radiologically. If initial dis-impaction was failed or not tolerated, shift to dis-impaction under general anesthesia.

Single 10 mg dose senna was given with the start of impaction. After dis-impaction; senna dose was increased if needed by 10 mg/clinic visit/week till achieving no soiling; Documentation of both initial effective starting dose and the time slipped till no soiling. Follow-up visits every month unless soiling recurs if soiling happens; additional dose (by 10 mg) was done. Treatment was continued for 6 months.

At the end of 6 months, the effective ending dose (maintenance dose) was documented.

Group B: Senna based laxative with massage

Laxative treatment as group A in addition to massage technique.

The massage technique was based upon the Tactile Stimulation Method of Birkestad that primarily consists of palm-to-skin stroking, gentle pressure and static touch (**Birkestad 1999**).

The patients lying in a comfortable relaxed supine position and physiotherapist performed slow circular clockwise movements on the abdomen, throw tangential pushing, with digital pulp, slow and gradual pressure, with fingers inclination 45

degrees (**Harrington & Haskvitz 2006**). The pressure applied to the abdomen on each point for 1 min, beginning with the ascending colon, transverse colon, descending colon and sigmoid; this sequence was repeated approximately 15 min. The therapist teaches the parents this technique and asked them to apply at home 3 times/day for 15 min.

Statistical analysis

The statistical analysis was conducted by using statistical SPSS Package program version 25 for Windows (SPSS, Inc., Chicago, IL). Data were normally distributed by using the Shapiro-Wilk test (parametric data). Additionally, testing for the homogeneity of variance revealed that there was no significant difference ($P>0.05$). Quantitative descriptive statistics included the mean and standard deviation for demographic data (age, weight, height, and BMI), constipation starting dose, constipation end dose, and time till not soiling variables. Qualitative descriptive statistics included number (percentage) for gender, area, breastfeeding, previous incomplete therapy for constipation, full urinary continence, fissure, psychosocial problems, developmental delay, and history of delayed passage of meconium variables. Using paired t-test to compare between rural area and the urban area within massage group and without massage group for constipation starting dose, constipation end dose, and time till not soiling variables. Using independent t-test to compare between massage group and without massage group for demographic data (age, weight, height, and BMI), constipation starting dose, constipation end dose, and time till not soiling variables. Also, to compare between two groups (massage group and without massage group) within the rural area and urban area for constipation starting dose, constipation end dose, and time till not soiling variables. Chi-square test used to compare between massage group and without the massage group for qualitative variables. All statistical analyses were significant at the level of probability ($P \leq 0.05$).

References:

Rasquin A1, Di Lorenzo C, Forbes D, Guiraldes E, Hyams JS, Staiano A, Walker LS. Gastroenterology. 2006 Apr;130(5):1527-37.

Mugie, S. M., Benninga, M. A., & Di Lorenzo, C. (2011). Epidemiology of constipation in children and adults: A systematic review. Best Practice & Research. Clinical Gastroenterology, 25, 3-18.

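### The arm letters are reversed between the Abstract and the Methods, the participant counts exceed the number evaluated by one, and the stated number randomised (86) cannot be confirmed

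*Combined protocol and SAP*

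**What the plan says.** **Arm key.** The Abstract states "Group (A) received abdominal massage with senna-based laxatives and group (B) received senna-based laxatives only". In Subjects and methods the headings read "Group A: Senna based laxative" and "Group B: Senna based laxative with massage", and the text under the second begins "Laxative treatment as group A in addition to massage technique". The Statistical analysis section uses no letters: "Using independent t-test to compare between massage group and without massage group for demographic data". The Abstract's result likewise reports improvement "in favor of massage group".

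**Participant flow.** Subjects and methods gives the starting number: "A total of one hundred and seventy children with overflow retentive stool incontinence were evaluated for eligibility". It continues: "Twenty-seven children did not complete the treatment course, fifty-eight child excluded due to unresponsiveness or non-compliance to our protocol". The same sentence ends by saying that 86 children were randomly divided into two groups. The Abstract also says that 86 were randomly assigned, but it describes those 86 as the children enrolled and checked for eligibility, a step for which Subjects and methods gives 170.

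**Exclusions and treatment.** Exclusion criterion (iv) covers children who failed to complete treatment, where cramping abdominal pain or vomiting occurred. The only treatment described is the arm treatment under the two group headings: an initial cleanout, then senna for 6 months, with or without massage. The documents name no analysis set and give no number per arm.

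**The concern.** There are three separate problems.

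First, a table, data file or figure labelled only A and B could be read in either direction, because the document supports both keys.

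Second, the counts that define the sample do not agree with each other, nor does the Abstract agree with the Methods on how many children were checked for eligibility.

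Third, and most important, the reasons given for the 27 and the 58 are not ordinary screening reasons. Not completing a course, not responding, and not complying can be seen only once treatment has begun. If those children had already been allocated, they were removed from a randomised comparison because of adherence or response. Response is close to the outcomes themselves (time until soiling stops and senna dose), so such removal can change the between-arm difference. Its direction cannot be judged without numbers per arm. The Abstract's claim of superiority for massage would then describe selected children, not all those randomised.

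**Working it through.** **Arm key, side by side**

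| Place | Group A | Group B |
|---|---|---|
| Abstract, Methods | massage + senna | senna only |
| Subjects and methods, group headings | senna only | senna + massage |

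The Methods version is not one mistyped heading. The Group B text defines its laxative treatment by reference to Group A and adds massage, which makes sense only if A is senna alone.

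**Flow count.** Inputs, all from Subjects and methods: 170 evaluated, 27 not completing, 58 excluded, 86 randomised.

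- Sum: 27 + 58 + 86 = 171. Excess over those evaluated: 171 − 170 = 1.
- By subtraction: 170 − 58 − 27 = 85, not 86; and 170 − 86 = 84, while 27 + 58 = 85.

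These are whole children, so rounding cannot explain the difference. Three disjoint groups drawn from 170 cannot total 171. Either at least one count is wrong, or at least one child is in more than one category. The documents do not show which.

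**What 86 might be.** The figures below are illustrative. Those with a loss assume that 86 is the number left after losses.

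| Assumption | Randomised | Lost after randomisation |
|---|---|---|
| All losses came before allocation | 86 | 0/86 = 0% |
| Only the 27 were lost after | 86 + 27 = 113 | 27/113 = 23.9% |
| Only the 58 were lost after | 86 + 58 = 144 | 58/144 = 40.3% |
| All 170 evaluated were randomised | 170 | (170 − 86)/170 = 84/170 = 49.4% |

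The one-child discrepancy hardly matters here. Counting down from 170 gives 170 − 58 = 112 and 26/112 = 23.2% for the second row, and 170 − 27 = 143 and 57/143 = 39.9% for the third. Using 171 in the last row gives 85/171 = 49.7%.

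A different reading keeps 86 as the number randomised and places the losses inside it. If the 27 are among the 86, then 27/86 = 31.4% were lost and 59 remain. If the 58 are, then 58/86 = 67.4% were lost and 28 remain. These readings leave 170 − 58 − 86 = 26 and 170 − 27 − 86 = 57 of those evaluated unexplained.

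**The case against.** The best case on the other side is that the text is literal and consistent on the key fact: both the Abstract and Subjects and methods say that 86 were randomised. The 27 and 58 come earlier in the sentence, as screening losses would. Non-compliance could refer to the initial cleanout, which both arms received, and criterion (iv) is limited to children with cramping pain or vomiting. A one-child excess could be a slip. The reversed letters do no harm where arms are named by treatment.

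Much of this stands. The statement that 86 were randomised is there, and the one-child excess does not by itself cast doubt on it; that doubt comes from how the losses are described. The order within a sentence is weak evidence of timing in either direction. The cleanout does not settle the matter, because it is described under the Group A heading as part of that arm's treatment, and no run-in before allocation is mentioned. Nor would it readily explain children who did not complete the treatment course.

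A reader might infer that the reported benefit belongs to the wrong arm. The documents do not support that: every stated contrast and the result name the arms by content. A reader might also infer that children were in fact dropped after randomisation. The wording makes that possible, but nothing establishes it.

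**Conclusion.** The point holds, and the text should be corrected. The arm key is reversed, with no demonstrated effect on a result. The flow counts exceed the number evaluated by 1, and the Abstract and Methods disagree (86 against 170) on how many were checked for eligibility. As a separate matter, the stated number randomised cannot be confirmed. If the 86 are the children left, loss after randomisation lies anywhere from 0% to 49.4% under the readings shown. The upper figure rests on the strong assumption that every child evaluated was randomised. The documents do not choose among these readings.

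The third element carries the weight. It decides whether the comparison is of all randomised children or of completers and compliers. The other two would be minor text corrections on their own.

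**What to change.** - Use one A/B mapping in the Abstract, the group headings and any coded file, checked against the allocation records.
- Reconcile 170, 27, 58 and 86 from source records. Correct the wrong count or state the overlap, and make the Abstract agree with Subjects and methods on the number checked for eligibility.
- State whether 86 is the number randomised or the number analysed, and whether the 27 and the 58 were lost before or after allocation. Give numbers randomised, lost (with reason) and analysed for each arm.
- If any were lost after allocation, make the main comparison one of all randomised children with available data, in their allocated arms. Otherwise, describe the result as a comparison of completers or compliers.
- If the records cannot settle a count, say so.

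The cost is a check of screening and allocation records plus text corrections, and a re-analysis if children were lost after allocation and their data exist. No new data collection is needed if the records were kept; the documents do not mention them, so that is an assumption.

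### The abstract's claim that both arms improved significantly has no planned test or pre-treatment measure behind it; the between-arm claim has a test but no planned estimate or interval

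*Combined protocol and SAP*

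**What the plan says.** The Abstract's Results sentence reads "Post-treatment there was a significant improvement in both groups in favor of massage group", followed by P < 0.05. It names no outcome and gives no estimate. The Conclusion says that massage with senna "has a great effect on children with overflow retentive stool incontinence than senna-based laxatives only".

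The Statistical analysis section lists the tests. The only paired one is described as "Using paired t-test to compare between rural area and the urban area within massage group and without massage group". Between arms, the plan is "Using independent t-test to compare between massage group and without massage group for demographic data", continuing to starting dose, end dose and time until soiling stops, and repeated within rural and within urban children. Chi-square tests compare the arms on qualitative variables. Summaries are means and standard deviations ("Quantitative descriptive statistics included the mean and standard deviation for demographic data", then the three outcomes). The threshold is P ≤ 0.05.

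Under Subjects and methods, the Group A treatment description says when outcomes are recorded: "Documentation of both initial effective starting dose and the time slipped till no soiling", and then the maintenance dose at six months.

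**The concern.** The Results sentence makes two claims: that each arm improved significantly, and that massage did better. They need different evidence. The within-arm claim needs a measure taken before treatment, the same measure taken afterwards, and a within-arm test. The between-arm claim needs a comparison of the arms. The plan supplies only the latter.

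A reader of the Abstract would take the within-arm claim as evidence that both regimens work. Nothing in the plan measures that, and a within-arm change has no untreated comparison, so it could not be credited to treatment even if it had been tested. The between-arm claim is what the trial was randomized to answer, but a reader is given a P value and the word *great* with no indication of how many milligrams or how much time is meant.

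**Working it through.** There is no figure to reproduce: the documents give a threshold P value but no mean, SD, arm size or exact P. The check is therefore a matching of claims to planned tests, followed by a short calculation of what a P value alone conveys here.

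**Step 1. Tests listed in the Statistical analysis section**

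- Paired t-test: rural versus urban, within each arm. This is not a change over time.
- Independent t-test: massage versus no massage, overall and by area, on starting dose, end dose and time to no soiling.
- Chi-square: massage versus no massage, on qualitative variables.

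None compares before with after, or starting dose with end dose, within an arm.

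**Step 2. When each outcome is recorded**

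- Time to no soiling: one value per child, reached on treatment. It has no earlier counterpart.
- Starting dose: the initial effective dose, reached by titration, so also an on-treatment value.
- End dose: recorded at six months.

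No soiling frequency, score or similar measure before treatment is described. Starting dose is the nearest thing to a baseline. But the written titration contains only increases: 10 mg steps until soiling stops, then a further 10 mg if it recurs. As written, end dose ≥ starting dose for every child, so a starting-to-end comparison could not show improvement as a falling dose, and no such test is listed in any case.

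**Step 3. Claims matched to tests**

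- Significant improvement within each arm: no planned test, no pre-treatment measure.
- Direction favouring massage, and the comparison with senna alone: planned, by independent t-test.
- Size (*great*): no planned mean difference, effect size or interval.

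**Step 4. What P < 0.05 says about size**

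Inputs: 86 randomized ("eighty-six child was divided randomly into two groups") and α = 0.05, both from the documents. Assumptions: two-sided test, outcomes for all 86, and 43 per arm, since neither arm sizes nor the allocation ratio is given.

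Half-width of the 95% CI, in pooled-SD units = t(0.975, n₁+n₂−2) × √(1/n₁ + 1/n₂). This is also the smallest observed difference that reaches P = 0.05.

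- 43:43: 1.989 × √(2/43) = 1.989 × 0.2157 = 0.43
- 40:46: 1.989 × √(1/40 + 1/46) = 1.989 × 0.2162 = 0.43
- 30:56: 1.989 × √(1/30 + 1/56) = 1.989 × 0.2263 = 0.45

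At 43:43, a result exactly at the threshold is 0.43 ± 0.43, that is 0.00 to 0.86 SD. A noncentral-t interval for the standardized difference gives the same limits to two decimals.

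**The case against.** Four points can fairly be made on the other side.

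First, a reader might infer from the missing before/after test that the Abstract's whole headline, Conclusion included, rests on no planned analysis. The documents do not support that. Both the phrase favouring massage and the comparison with senna alone are between-arm statements, and the independent t-tests on end dose and time to no soiling address them directly. This stands and limits the point to the within-arm claim and to the missing estimate.

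Second, *great* followed by *than* is ungrammatical and may be a slip for *greater*; the document has other slips of language. Read that way, the sentence states a direction and makes no claim about size. This is plausible, and the text cannot settle it. Either way, the reader still has no estimate.

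Third, an interval touching zero at P = 0.05 is true of any trial of any size, and the actual P value is unknown. That is correct: the 0.00 to 0.86 SD range illustrates what a bare P value leaves open and is not the trial's result. A reader should not infer that the massage effect is small or absent. What is specific to this trial is the half-width of about 0.43 SD.

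Fourth, the document has no results section, so intervals may have been reported elsewhere, and the planned means and SDs would let a reader derive them once arm sizes are known. This stands, but the plan does not call for them and the Abstract does not give them.

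One might also say that children who entered with soiling and reached no soiling have plainly improved. That is a description and carries no P value. It is also affected by selection: 58 children were excluded for unresponsiveness or non-compliance and 27 did not complete treatment.

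**Conclusion.** The point holds in two parts. The within-arm statement is wrong as written: no listed test and no recorded pre-treatment value could produce it, and this rests on no numerical assumption. The between-arm statement has a planned test, but the plan provides no estimate or interval, so P < 0.05 supports a direction only. For scale, the uncertainty on a mean difference is about ±0.43 SD at 43:43 or 40:46 and ±0.45 SD at 30:56, assuming a two-sided test and complete outcomes.

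This is a correction to what is reported and concluded. It does not invalidate the planned between-arm comparison, and it implies nothing about the true size of the massage effect. It should be made because these sentences are what most readers will take from the trial.

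**What to change.** - **Delete the within-arm improvement claim** from the Abstract. If a pre-treatment measure was in fact collected, it could instead be described, with its test, and labelled as an addition to the plan.
- **Add to the Statistical analysis section** the between-arm mean difference with 95% CI for time to no soiling (in days or weeks) and for starting and end dose (in mg), with the number analysed in each arm.
- **Replace *great effect*** in the Conclusion with those estimates. Give each difference by treatment name, since the letters A and B are assigned to opposite treatments in the Abstract and in Subjects and methods.
- **Report all three outcomes.** The documents name no primary outcome, recruitment and treatment are described as ending in March 2019, and the document dated 02/12/2020 already states results. Singling one out now would be post hoc and should be labelled so.

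The cost is small: wording in two sections, and intervals that SPSS prints with the t-test. The headline becomes more modest.

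### Half of the evaluated children (85 of 170) left for non-completion, non-response or non-compliance, with timing relative to randomisation unsettled, no analysis set, and no rule for a randomised child who never stops soiling

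*Combined protocol and SAP*

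**What the plan says.** All references are to the combined protocol and SAP.

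- **Subjects and methods, participant flow.** "A total of one hundred and seventy children with overflow retentive stool incontinence were evaluated for eligibility". Then: "Twenty-seven children did not complete the treatment course, fifty-eight child excluded due to unresponsiveness or non-compliance to our protocol". The same sentence ends: "eighty-six child was divided randomly into two groups".
- **Subjects and methods, exclusions.** The list opens with "Other children were excluded from our study as they met one of the following criteria". Items (i), (ii), (iii) and (v) are suspected Hirschsprung's disease, anorectal malformation, organic obstruction and need for bowel surgery. Item (iv) is different in kind: "children failed to complete treatment (if cramping abdominal pain or vomiting occurred".
- **Abstract, Methods.** "Eighty-six children with overflow retentive stool incontinence enrolled in this study and were assessed for eligibility", followed by "They were assigned randomly into two groups".
- **Group A.** The only treatment course defined stands under the arm headings: "Treatment was continued for 6 months". The dose is raised until soiling stops, and the time taken to reach that point is recorded. Recurrence of soiling is foreseen. The ending dose is recorded at 6 months.
- **Statistical analysis.** Independent t-tests compare the arms on starting dose, end dose and time until soiling stops. The section gives no analysis set, no missing-data method and no rule for a child still soiling at 6 months. It lists no tolerability variable.

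**The concern.** Non-completion, non-response, non-compliance, and stopping for cramping or vomiting become known only once treatment is under way. The plan uses them to decide who is in the study, but describes no treatment phase before randomisation in which they could have been observed.

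What is at stake depends on when the children left.

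- **After randomisation.** The t-tests compare children selected on response, compliance and tolerance. Response is the outcome itself. The groups compared are then no longer the groups that were randomised, and a difference between arms in stopping for cramping or vomiting would go unreported.
- **Before randomisation.** The arms remain comparable. However, the abstract states its conclusion for affected children in general, while the trial would have enrolled only those who had passed an undescribed first phase.

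A second problem does not depend on timing. Time until soiling stops exists only for a child who stops soiling, so a randomised child who never does has no value to enter in the t-test. Likewise, because the ending dose is recorded at 6 months, a randomised child who left earlier has no ending dose. This is an inference from how the variables are recorded; the plan gives no rule for either case.

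**Working it through.** **Inputs.** From Subjects and methods: 170 evaluated, 27 not completing, 58 excluded, 86 randomised. From the abstract: 86 assessed. No count is given by arm, and the 58 are not split between non-response and non-compliance.

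**Step 1: the plan's own total.** 27 + 58 + 86 = 171, against 170 stated. The flow does not reproduce. The abstract's 86 assessed also conflicts with 170 evaluated.

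**Step 2: share removed.** 27 + 58 = 85, and 85/170 = 50.0%. Of this, 27/170 = 15.9% is non-completion and 58/170 = 34.1% is non-response or non-compliance. With 171 as the denominator the share is 85/171 = 49.7%. If 170 and 86 are both right and the counts do not overlap, it is 84/170 = 49.4%.

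**Step 3: loss after randomisation.** If the 86 are the children left after all removals, and k children were removed after randomisation, the loss is k/(86 + k). If the 27 are part of the 86, the loss is 27/86.

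| Reading | Calculation | Loss |
|---|---|---|
| All 85 left before | 0/86 | 0% |
| Only the 27 left after | 27/(86 + 27) = 27/113 | 23.9% |
| The 27 are among the 86 | 27/86 | 31.4% |
| Only the 58 left after | 58/(86 + 58) = 58/144 | 40.3% |
| All 85 left after | 85/(86 + 85) = 85/171 | 49.7% |

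On the third reading 86 - 27 = 59 children remain and 170 - 58 - 86 = 26 are unaccounted for.

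**Step 4: effect of the one-child mismatch.** Forcing the total to 170 by changing one count changes little:

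- 27 to 26: 26/112 = 23.2%, 58/144 = 40.3%, 84/170 = 49.4%.
- 58 to 57: 27/113 = 23.9%, 57/143 = 39.9%, 84/170 = 49.4%.
- 86 to 85: 27/112 = 24.1%, 58/143 = 40.6%, 85/170 = 50.0%.

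**Step 5: the other exclusions.** If the counts do not overlap, they use up all 170 and leave no child for (i), (ii), (iii) or (v). If the 27 are among the 86, the 26 unaccounted for could be those exclusions.

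**Step 6: what a t-test among responders can see.** This is an illustration on assumed inputs, not an estimate for this trial: 85 randomised per arm, failures dropped, and the same time distribution among responders in both arms (normal, mean 6, SD 2; 4,000 runs).

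| True failure rates | t-test rejects | Power comparing success proportions |
|---|---|---|
| 40% v 60% | 5.4% | 74.6% |
| 30% v 70% | 5.1% | close to 100% |

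Under these assumptions the t-test rejects at about its nominal 5%, however far apart the failure rates are. If failures were dropped after randomisation, it would not register a difference in failure.

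**The case against.** The strongest reply is that the text favours removal before randomisation. The 27 and 58 are listed first and the 86 are then divided at random; the abstract likewise has 86 enrolled and assigned. The near match of 170 - 85 = 85 with 86 points the same way. Being known only after treatment starts is not the same as being known only after randomisation. On this reading no randomised child is lost and the arms are comparable. This stands as the favoured reading, but it is not settled: no earlier phase is described, and the only course a child could fail to complete is the 6-month one under the arm headings.

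A reader might infer that the t-test on time omits treatment failures whatever the timing. The documents do not support that. If all 85 left first, the unresponsive children were already gone, and the dose was then raised until soiling stopped, so all 86 may have a recorded time. What holds on any timing is only that no rule covers a child who never reaches that point.

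A reader might also infer that the counts prove no child was excluded under (i), (ii), (iii) or (v). That assumes the counts do not overlap, and that the other excluded children lie within the 170. Neither is stated.

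Finally, prior removal would not show that the 86 tolerated the study treatment. Tolerating an earlier phase says nothing certain about the later 6 months, and no massage before randomisation is described.

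**Conclusion.** The concern holds in this form. Half of the evaluated children (85 of 170, 50.0%) left for reasons known only after treatment starts. The timing relative to randomisation is unsettled, no analysis set is named, and the flow is inconsistent (171 against 170, and 86 assessed against 170).

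Loss after randomisation lies between 0% and 49.7% on the readings considered. The 0% figure rests on the word order; the others rest on there being no described run-in. Partial splits of the 85 fall within the same range.

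To the extent that removal followed randomisation, the t-tests may be biased. Neither size nor direction can be computed, because the split by arm is not given. A reader might suppose that more children were removed from one arm and that this produced the result favouring massage; that is possible, but nothing in the documents shows it. To the extent that removal came first, the comparison stands and the abstract's conclusion is too broad.

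Whether any of the 86 never stopped soiling is not stated, so the missing rule is a gap in the plan and not a demonstrated omission. The reported advantage for massage cannot be interpreted securely until the flow is settled.

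**What to change.** (a) **Flow.** Reconcile 170 with 171 and with the abstract's 86. Report the number randomised per arm, naming arms by treatment because the abstract and the methods reverse the labels A and B. Report the 27 and the 58 by arm, reason and timing, with non-response separate from non-compliance and with cramping and vomiting shown. State how many children were excluded under (i), (ii), (iii) and (v), and whether they are within the 170.

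(b) **Removals after randomisation.** Do not use non-response, non-compliance or failure to complete as a reason to leave the analysis. Analyse all randomised children in the assigned arm and keep the completer t-tests as a sensitivity analysis.

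(c) **Time outcome.** If any randomised child never stopped soiling, or left before doing so, analyse time to the first point of no soiling as time-to-event (Kaplan-Meier, log-rank):

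- Children who never reached it are censored at 6 months.
- Children who left before reaching it are shown both ways: censored at last contact, and kept event-free to 6 months.
- Children who reached it and later relapsed or left keep their event.

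If every randomised child reached it, say so; the t-test then omits no one. Report doses descriptively, with the number lacking a value per arm.

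(d) **Removals before randomisation.** Describe that phase and limit the conclusion to children who had passed it.

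(e) **Unrecorded data.** If arm or outcome was not recorded for children who left, say so and limit the conclusion.

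**Cost.** A flow table, a stated analysis set and some re-analysis of existing data. The study ran to March 2019, so no new patients are needed. The documents do not show that arm or later soiling status was kept for children who left; without it, (b) cannot be done for them and (c) is confined to the 86. The estimate may become less favourable.
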